### SAE Reporting

All SAEs must be reported within 24 hours to the Study Coordinator and to enable reporting to the Guinean Ministry of Health within 7 calendar days of identification. All SAEs must also be reported within 24 hours to BiogenIdec Inc. at [[contact]](mailto:[contact]) or by FAX at [contact].

All AEs and SAEs will be evaluated by the investigator or delegate for causal relationship to the investigational product.

### 8.4 Evaluation of Safety

Safety will be assessed by comparing the occurrence of SAEs and of clinically important adverse events (moderate and severe) attributable to the intervention. Safety monitoring for this interventional study will involve collection of data with direct comparison between IFN  $\beta$ -1a-treated patients and those not receiving IFN  $\beta$ -1a.

Study stopping rules:

- A patient dies during therapy as a result of an SAE assessed as related to the investigational product.

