### 9.2 Secondary

**Safety:** Occurrence and severity of adverse event; time to onset, duration (number of days), severity, and seriousness of solicited and non-solicited injection site reactions and systemic adverse events occurring up to 7 days after the last injection. Occurrence, nature, time to onset relative to the first IFN  $\beta$ -1a dose, duration, severity, relationship to injection of SAEs throughout the trial.

- The frequency of clinically important (moderate or severe) adverse events will be compared between the groups
- The frequency of serious adverse events will be compared between the groups.

Parameters to look for adverse events will be solicited such as local injection site erythema and swelling, fever, heart rate, blood pressure, and rash.

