## 10.2 Statistical analyses and methods

Demographics, and underlying conditions will be described by means and standard deviation for continuous variables, by median and interquartile range for ordinal or count variables, and by frequencies and percentages for categorical variables. Endpoints will be described and compared between treatment and usual standard of care groups using cross-tabulation tables and Fisher's Exact test for categorical variables, t-test for normally distributed continuous variables and Wilcoxon non-parametric test for non-normally distributed continuous or ordinal variables.

Safety variables such as fever will be considered in three different formats:

1. As ordinal, representing various levels of severity of the symptom. For instance, fever will be described as "none", "mild", "moderate", or "severe".
2. As binary, considering only the presence vs. the absence of the symptom.
3. As binary, considering the most serious expression of the symptom. For instance by grouping "moderate" and "severe" together.

Separate analyses for time periods of 0-3, 4-7, and 8-10 days will be conducted. For each of these time periods the most severe report of the AE for each participant will be counted.

Adverse Events and Serious Adverse Events will be considered in two ways: presence of any event and presence of any event related to the treatment.

Symptoms will be assessed as a repeated measure using GEE modelling.

Survival will be analyzed using a Kaplan-Meier curve and Cox-proportional hazard modeling with 2 week and 1 month survival rates determined.

Viral clearance will be analyzed as binary variables for detection (presence) or non-detection (absence) as well as continuous variables where applicable (e.g. quantitative RT-PCR measurements).

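### Section 8.4 compares IFN-attributable events between treated and untreated patients, although the untreated count is zero by definition, and this conflicts with the all-cause comparisons in section 9.2

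*Protocol*

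**What the plan says.** Section 8.4 (Evaluation of Safety) gives the criterion: "Safety will be assessed by comparing the occurrence of SAEs and of clinically important adverse events (moderate and severe) attributable to the intervention". Its next sentence makes this a direct comparison of patients given IFN β-1a with "those not receiving IFN" β-1a.

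Causality is defined in section 8.3 (SAE Reporting): "All AEs and SAEs will be evaluated by the investigator or delegate for causal relationship to the investigational product".

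Section 9.2 lists two between-group safety endpoints with no causality condition: "The frequency of clinically important (moderate or severe) adverse events will be compared between the groups" and "The frequency of serious adverse events will be compared between the groups". The synopsis has the same two. Section 9.2 also says: "Parameters to look for adverse events will be solicited such as local injection site erythema and swelling, fever".

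Section 10.2 gives comparison of the treatment and usual-care groups as its general method for endpoints, with Fisher's exact test for categorical variables. It then has adverse events and SAEs analysed in two ways: "presence of any event and presence of any event related to the treatment". The synopsis repeats that sentence.

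**The concern.** A between-group safety comparison should estimate how many more events occur with the drug than without it. An event counts as attributable only if an investigator links it to IFN β-1a, and no such link is possible for a patient who never received it. Injection-site reactions raise the same problem: the comparators get no injection, so they cannot have one.

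The comparator count is therefore fixed at zero before any data are seen, and the contrast measures only how often investigators blame the drug in treated patients. Section 8.2 (Adverse Events) concedes that drug effects and symptoms of the infection may be hard to tell apart, so that judgement is error-prone in the only group where it counts.

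Section 16 names safety as a determining factor for extending the pilot. A reader of 8.4 and a reader of 9.2 would bring different safety results to that decision.

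**Working it through.** **Side by side**

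| Place | Events compared | Attribution required? |
|---|---|---|
| Synopsis, secondary endpoints | Moderate or severe AEs; SAEs | No |
| 8.4 | Moderate or severe AEs; SAEs | Yes for AEs; SAEs depend on how the sentence is read |
| 9.2 | Moderate or severe AEs; SAEs | No |
| 10.2, first way | Any AE or SAE | No |
| 10.2, second way | Related AE or SAE | Yes |

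No sentence ranks these or says which one section 16 uses.

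**Inputs.** The protocol plans 30–50 treated patients (10.1) and names Fisher's exact test (10.2). It gives no significance level, comparator size or safety event rate, so there is no protocol figure to reproduce. Assumed here: two-sided 5%; comparators 1:1, with 1:2 as a variant; background risk of a moderate or severe event 20%, 50% or 80%; share of patients with an event in whom it is wrongly attributed to IFN β-1a 10% to 50%.

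**Step 1: how many attributed events reach p<0.05 against zero?** For r of n against 0 of n, the two-sided Fisher p is 2·C(n,r)/C(2n,r).

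- 6/30 v 0/30: 2 × 593,775 / 50,063,860 = 0.024
- 5/30 v 0/30: 2 × 142,506 / 5,461,512 = 0.052
- 6/50 v 0/50: p = 0.027
- 5/50 v 0/50: p = 0.056

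Six are needed at either size. With twice as many comparators, three are enough (3/30 v 0/60, p=0.035; 3/50 v 0/100, p=0.036).

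**Step 2: how often does that happen when the drug adds no risk?** Let b be the background risk and q the wrongly attributed share. The number of treated patients with an attributed event is binomial(n, b·q). The chance of a significant result against IFN β-1a is P(X ≥ 6), with 1:1 groups:

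| n per group | b | q=10% | q=20% | q=30% | q=50% |
|---|---|---|---|---|---|
| 30 | 20% | about 0% | 0.1% | 0.8% | 7.3% |
| 30 | 50% | 0.3% | 7.3% | 28.9% | 79.7% |
| 30 | 80% | 2.9% | 34.5% | 76.0% | 99.4% |
| 50 | 20% | about 0% | 1.4% | 7.8% | 38.4% |
| 50 | 50% | 3.8% | 38.4% | 78.1% | 99.3% |
| 50 | 80% | 20.8% | 83.2% | 98.9% | about 100% |

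The chance of at least one attributed event, which already gives a difference against the drug, is 1 − (1 − b·q)^n. It runs from 1 − 0.98^30 = 46% to nearly 100%.

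**Step 3: the opposite error.** If investigators put drug effects down to Ebola, the attributed count falls. Five of 30 treated patients (17%) still gives p=0.052, so a real excess could go undetected.

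**Step 4: the all-cause comparison under the same conditions.** With no true excess and 1:1 groups, the chance of a significant Fisher result in either direction is 2.2%–2.7% at 30 per group and 2.8%–3.5% at 50, across the three background risks. It stays below 5% and does not depend on q.

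**The case against.** The strongest reply is that the sound comparison is already planned. The synopsis and 9.2 compare all SAEs and all moderate or severe adverse events, the first way in 10.2 is all-cause, and section 8.3 defines an adverse event without requiring causality. On this view 8.4 is one loosely worded sentence, and its causality qualifier may attach only to the adverse events, leaving SAEs all-cause as in 9.2.

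Much of this stands. A reader might infer from 8.4 that safety is judged only on attributable events. The documents do not support that, because the all-cause endpoints are explicit. A reader might also infer that the comparison is bound to show harm whatever the truth. That does not follow either: steps 1 to 3 show that the result depends on how many events are attributed. Nor does section 16 say that a test of related events decides extension; it names safety in general terms.

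It would be tempting to size the problem from the flu-like symptom rates in section 8.2. Those come from multiple sclerosis patients given the drug intramuscularly and are not limited to moderate or severe events, so they do not describe this trial and are not used here.

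The reply does not remove the defect. The section headed as the evaluation of safety states a different criterion from the endpoint section. The adverse-event part of it fails on either reading of the sentence. The second way in 10.2 sits under a between-group method with no exception made for it.

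**Conclusion.** The point holds as an inconsistency that includes one uninformative comparison. As written, the contrast in 8.4 cannot estimate the excess risk from IFN β-1a, and neither can the related-event analysis in 10.2 if it is run between groups. The difference can only be nil or unfavourable to the drug. With no true excess, the chance of a significant result against it ranges from about 0% to nearly 100% over the assumed background risks and attribution shares. Under-attribution could equally conceal harm.

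These figures rest on assumed equal groups, a two-sided 5% level and assumed event and attribution rates, none of which the protocol gives. The structural zero needs none of those assumptions.

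Severity is moderate: the all-cause comparisons are already endpoints, so the safety plan as a whole does not fail.

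**What to change.** - **Section 8.4:** align with 9.2. State that the between-group safety comparison uses all SAEs and all moderate or severe systemic adverse events, regardless of attribution. Limiting it to systemic events keeps injection-site reactions out of a comparison in which untreated patients cannot have them.
- **Section 10.2, and the matching sentence in the synopsis:** state that events judged related to IFN β-1a, and injection-site reactions, are reported descriptively in the IFN group only, with no test against the comparators.

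The cost is a few sentences. No new data are needed and no clinical management changes. The downside is that an all-cause comparison carries the background of Ebola events in both groups and is less sensitive to a drug effect. The descriptive account of related events in treated patients should therefore be kept beside it.

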### 6.5 Follow-up

Collection from daily recordings will be undertaken either prospectively or retrospectively to assess adverse event and efficacy of therapy from day 1 (1st day of treatment) to day 10 and then weekly while admitted to the treatment centre and then 30 days post last dose. For patients for whom therapy is discontinued prior to day 10, assessments will follow the same schedule to allow comparison of disease course.

The following will be recorded, as permitted, starting immediately prior to the onset of administration of IFN  $\beta$ -1a, then on a daily basis whilst the patient is in the treatment centre:

- Temperature; fever will be defined as a temperature  $\geq 38$  °C.
- Concurrent illness symptoms: chills, myalgia, cough, sore throat, nausea, vomiting, diarrhea, hemaorrhage.
- Adverse events will be recorded per protocol. Medication history at baseline and daily will be recorded.
  - Blood samples:
    - 20 cc of Blood for virologic measurement (if feasible).
    - A convalescent serum (10 cc tiger top tube) will be obtained at 1 month (when possible).
  - Survival

Of note, it is expected that there will be missing data points for study participants depending on the clinical care data available in the medical chart and residual blood samples available for testing.

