### **Rare Adverse Events (<1% frequency)**

Severe psychiatric adverse events may develop in persons receiving therapy with IFN  $\beta$ -1a and includes suicidal ideation and suicide. The risk of this happening is small and less than 1%.

IFN- $\alpha/\beta$  has on occasion exacerbated pre-existing cardiovascular disease, and has caused angina (chest pain), rhythm disturbances or heart attacks (myocardial infarction) in these persons. In those with known pre-existing heart disease, physicians will monitor for cardiac symptoms closely and discontinue IFN  $\beta$ -1a if cardiovascular symptoms appear to be worsened by the drug.

IFN  $\beta$ -1a has rarely been associated with ophthalmic problems, including retinal hemorrhages, optic neuritis and papilledema in persons on long-term treatment. Participants will be asked to report to their physician any disturbance in vision while they are on treatment.

IFN  $\beta$ -1a may exacerbate liver disease and will be discontinued with grade 4 hepatotoxicity.

Very rarely IFN  $\beta$ -1a has been associated with pulmonary syndromes including pneumonia and worsening of asthma. If a participant develops worsening pulmonary symptomatology, which is felt to be due to IFN  $\beta$ -1a then the drug will be dose-reduced or stopped.

IFN  $\beta$ -1a may aggravate autoimmune diseases (for example, systemic lupus or rheumatoid arthritis), and those with pre-existing autoimmune disease will be closely monitored.

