### **Management of Adverse Events**

Management of adverse events is generally achieved by dose reduction of IFN  $\beta$ -1a, however, in the case of life-threatening adverse events, development of cardiac dysfunction, or precipitous decline in pulmonary function over a 24 hour period, which is not explained by disease progression and which may be associated IFN  $\beta$ -1a, therapy will be discontinued.

Flu-like symptoms can be treated with acetaminophen 500-1000 mg or ibuprofen 200-400 mg 30 minutes before IFN  $\beta$ -1a injection.

The following guidelines will be used to determine when dose modification of the investigational product for an adverse event should be implemented.

- Grade I (mild) adverse events: No dosage adjustment
- Grade 2 (moderate) adverse events: No dosage adjustment
- Grade 3 (severe) adverse events: Patients who develop grade 3 adverse events (except flu like symptoms, unless they are incapacitating) should have IFN  $\beta$ -1a reduced to 3 MIU (15 mcg). Alternatively, IFN  $\beta$ -1a may be discontinued.

- Grade 4 (Life threatening) adverse events (SAE): IFN  $\beta$ -1a will be discontinued.

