### 8.3 Adverse Event Definitions and Reporting

Adverse Event (AE): is any untoward medical occurrence in a patient or clinical investigation participant administered a product. It does not necessarily have to have a causal relationship with this treatment. An AE can therefore be any unfavorable and unintended sign (including an abnormal laboratory finding, for example), symptom or disease temporally associated with the use of a medicinal product, whether or not considered related to the medicinal product.

All adverse events will be recorded and transcribed into the CRF. Solicited AEs and non-solicited AEs will be collected daily for the first four days and then every 2-3 days during therapy, or whenever reported by patients. SAEs will be collected while on study medication and for 30 days after administration of the last dose.

**Serious Adverse Event (SAE):** is any adverse event that:

- is fatal
- is life-threatening
- results in persistent or significant disability/incapacity
- requires initial hospitalization or prolongation of existing hospitalization
- causes congenital anomalies or birth defects

The term "life-threatening" refers to an event in which the patient was at risk of death at the time of the event. It does not refer to an event, which hypothetically might have caused death, if it were more severe. All deaths occurring while on protocol therapy or within 30 days of the last dose, should be reported (see below).

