## 12. Premature Discontinuation of Treatment

Participants may withdraw from the study at any time for any reason without jeopardy to their current or future care. The investigator may also withdraw patients from the study without the participant's permission in the event of intercurrent illness, adverse events, treatment failures, protocol violation, administrative reasons, or any other reasons. The reason for withdrawal should be clearly documented in the CRF.

Specific criteria for premature discontinuation of treatment will also include, progression of disease due to IFN  $\beta$ -1a or grade IV adverse events felt to be due to IFN  $\beta$ -1a. If the reason for removal of a patient from the study is an adverse event or abnormal laboratory result, the

principal specific event or test will be documented completely on the CRF. A participant will be withdrawn if at any time, in the opinion of the investigator, study participation would not be in the best interest of the participant.

Participants may withdraw or be withdrawn from treatment and this will not automatically lead to withdrawal from the rest of the study. These participants would continue to be followed per protocol for safety and disease course, off therapy. Unnecessary withdrawal of patients should be avoided.

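### The only study stopping rule covers related deaths during therapy, so it misses a related death after interferon has been withdrawn for a life-threatening event

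*Protocol*

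**What the plan says.** Section 8.4 has one bullet under its study stopping rules: "A patient dies during therapy as a result of an SAE assessed as related to the investigational product".

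Three places take an individual patient off the drug for severe toxicity:

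- Section 8.2, on rare adverse events, says IFN β-1a "may exacerbate liver disease and will be discontinued with grade 4 hepatotoxicity".
- Section 8.2, on managing adverse events, requires discontinuation for "Grade 4 (Life threatening) adverse events (SAE): IFN" β-1a.
- Section 12 lists among its discontinuation criteria "grade IV adverse events felt to be due to IFN" β-1a.

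A patient taken off the drug stays in the study. Section 12 states: "These participants would continue to be followed per protocol for safety and disease course, off therapy". Section 6.5 adds: "For patients for whom therapy is discontinued prior to day 10, assessments will follow the same schedule to allow comparison of disease course".

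The safety capture window in Section 8.3 is wider than that of the stopping rule. For serious events: "SAEs will be collected while on study medication and for 30 days after administration of the last dose". For deaths: "All deaths occurring while on protocol therapy or within 30 days of the last dose, should be reported (see below").

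**The concern.** A grade 4 event attributed to the drug is a likely route to a drug-related death, and it is also what requires the drug to be stopped. A site that follows the withdrawal rule promptly moves the patient outside the only defined study stop while the outcome is still open. A site that is slow to withdraw leaves the patient inside it. Whether a related death halts the study then depends on how quickly dosing ceased, which has no safety rationale.

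Section 2.3.3 says IFN β-1a has not been given to patients with this infection before. A predefined stop should therefore cover the route to a related death that the protocol's own management rules create.

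**Working it through.** The protocol gives no figure for this rule, so there is none to reproduce. The check is a reading of the text, followed by simple arithmetic on the windows.

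**1. What the timing condition attaches to.** In the Section 8.4 bullet, *during therapy* qualifies the verb *dies*. The onset of the serious event and the last exposure do not decide whether the rule applies.

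**2. When therapy ends.** The protocol never defines therapy formally. Section 12 describes withdrawn patients as off therapy, and Section 6.5 describes therapy as discontinued before day 10. Both uses place the end of therapy at withdrawal, not at the end of the planned course. Section 8.3 names time on therapy and the 30 days after the last dose as two periods. That fits this reading but does not prove it. The stopping rule refers only to the first period.

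**3. The sequence.** A related grade 4 event leads to discontinuation (Sections 8.2 and 12), then to follow-up off treatment (Sections 6.5 and 12). If the patient then dies of that event, the condition in Section 8.4 is not met.

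**4. Length of the windows.** Inputs are a planned course of 10 days (Section 6.3) and capture for 30 days after the last dose (Section 8.3).

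| Last dose on | Rule can trigger through | Capture runs through | Planned treatment days after the last dose |
|---|---|---|---|
| Day 3 | day 3 | 3 + 30 = day 33 | 10 − 3 = 7 |
| Day 5 | day 5 | 5 + 30 = day 35 | 10 − 5 = 5 |
| Day 10 | day 10 | 10 + 30 = day 40 | 0 |

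Days 3 and 5 are illustrations, not risk estimates. They were chosen because Section 8.1 does not expect stabilization before day 3-5. The day 10 row is a weaker case, because Section 6.3 expects patients to stop at discharge or about 48 hours before it.

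**5. Whether the drug could still act after withdrawal.** Section 7.2 gives an elimination half-life of 19 h (range 8-54 h) in healthy subjects. It also says response markers stay raised for at least 4 days after a dose. Taking five half-lives as a conventional multiple (an assumption), counted from the peak:

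- 5 × 19 h = 95 h = 4.0 days
- 5 × 8 h = 40 h = 1.7 days
- 5 × 54 h = 270 h = 11.3 days

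This supports some coverage after the last dose. It does not establish 30 days; that length rests only on matching Section 8.3.

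**The case against.** **The reading.** Therapy is undefined, and Section 6.2 describes days 1-10 as days of therapy and/or in-hospital follow-up. A sponsor could say the rule meant that whole window. Section 8.3 is compatible with either reading. This is fair, but Sections 6.5 and 12 point the other way, and a stopping rule should not depend on a contested reading.

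**Other safeguards.** There are several:

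- Serious events reach the Study Coordinator and the manufacturer within 24 hours and the Ministry of Health within 7 calendar days, with a causality assessment (Section 8.3).
- They also go to the ethics committee (Section 14).
- Among the first ten treated patients, the next one waits until the previous one has had five doses (Section 2.3.2). Read literally, withdrawal after three doses would hold the next start.
- Section 12 allows discontinuation on new product data or regulatory advice.
- Safety bears on the decision to extend the study (Section 16).

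So neither detection nor the power to stop is missing. What is missing is a required stop. The stagger delays first doses, does not hold enrolment once five doses have been given, and is designed for the first ten patients only. The other provisions inform a decision or permit a stop.

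**False stops.** The rule fires on one death. Section 1.1 gives a fatality of 57-90%. If mortality were unchanged, 30 to 50 patients would mean roughly 17 (0.57 × 30) to 45 (0.90 × 50) deaths, each needing a causality judgement. Section 8.2 concedes that drug effects and the underlying condition may be hard to separate. A wider window raises the chance of stopping on a misattributed death. This stands as a real cost. The relatedness condition limits it, and the same difficulty already affects deaths on treatment.

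**Conclusion.** The concern holds. As written, the only predefined study stop does not apply to a related death that follows the withdrawal the protocol itself requires. This is not a contradiction with the reporting window in Section 8.3; the stopping rule's own window is set too narrowly.

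The practical difference is between a mandatory and a discretionary stop for such deaths. Their frequency cannot be derived from the protocol. The conclusion assumes that therapy ends when the drug is withdrawn, which is how Sections 6.5 and 12 use the term. It should be fixed because the point concerns patient safety and the remedy is cheap. No endpoint or efficacy analysis is affected.

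**What to change.** In Section 8.4, extend the timing condition so that the rule applies when a patient dies on treatment, or in the 30 days after the last dose, from a serious adverse event assessed as related to IFN β-1a. State that this applies whether the course was completed or stopped early.

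The trigger window then runs from k to k + 30 days for a patient whose last dose is on day k, and from at most 10 to about 40 days for a full course. Only one line of wording changes. Serious events and deaths are already collected over this window, and serious events are already assessed for causality (Section 8.3). The price is a rule that will fire somewhat more often, including on some Ebola deaths wrongly judged related; the protocol gives no basis for quantifying this.

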### **2.3.2 Procedures to Minimize Risks**

Alcohol swabbing of the skin prior to venipuncture and IFN  $\beta$ -1a injection, and use of sterile disposable needles and syringes will minimize the risk of infection. Applying pressure over needle puncture sites to minimize bruising should also be carried out. Exclusion of patients who have previously experienced a severe allergic reaction to IFN  $\beta$  preparations, and since participants will probably remain in the treatment centres for the duration of treatment, trained personnel will be available in case for allergic reactions post-injection.

For the first ten (10) ebola-infected subjects to receive IFN  $\beta$ -1a, a staggered administration schedule will be used to minimize the effect of any unforeseen serious adverse events in this patient population. The second patient will not be administered IFN  $\beta$ -1a until the first subject has received five (5) doses. Likewise, the third subject will not be administered IFN  $\beta$ -1a until the second subject has received 5 doses. If, in the opinion of the treating physician and the Special Access Program in Conakry, Guinea, no unforeseen serious adverse events are observed five (5) days after the tenth subject has received IFN  $\beta$ -1a, more than one of the remaining

subjects enrolled/to be enrolled in the study may receive their first dose of IFN  $\beta$ -1a on the same day.

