## **8. Management of Ebola Disease Progression, Adverse Events and Serious Adverse Events**

### **8.1 Ebola Disease Progression**

It is expected that the disease will continue to progress for the initial 24-72 hours of therapy. Stabilization or improvement is not anticipated to manifest until day 3-5. Considering the potential adverse events of IFN  $\beta$ -1a therapy, special consideration will be placed to determine whether the treatment regimen adversely affects disease progression.

If the participant progresses at  $\geq 48$  hours while being treated with IFN  $\beta$ -1a in terms of worsening of disease symptoms and if this progression is felt by the treating physician to probably be related to the treatment regimen, then IFN  $\beta$ -1a will be either decreased in dose or discontinued.

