### **8.2 Adverse Events Management**

It is expected that IFN  $\beta$ -1a will have a direct antiviral effect if initiated early in the course of illness and will have an immunomodulatory effect on exaggerated inflammatory responses observed in ill patients. It is likely that this drug will cause certain flu-like symptoms or symptoms compatible with disease progression but it is unlikely that these symptoms will be serious with the short 10-day-course. If there is concern that IFN  $\beta$ -1a is associated with worsening of disease, it may be dose-reduced or treatment stopped.

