#### **Adverse Events**

This section is extracted from the product monograph and is supplementary information to that provided in section 2.3 of the protocol. The side effects listed are based on a phase 3 study with 9 or 15  $\mu$ g of IFN  $\beta$ -1a given three times a week for 24-48 weeks. Since IFN  $\beta$ -1a is given for 10 days in this study, the safety information, listed in section 2.3 for 10 days of therapy, may be more relevant.

The most common adverse events of AVONEX reported in placebo-controlled studies (IM administration) are listed below with the incidence in placebo-treated multiple sclerosis patients listed first and AVONEX-treated multiple sclerosis patients listed second: headache (55%, 58%), flu-like symptoms (29%, 49%), pain (21%, 23%), asthenia (18%, 24%), fever (9%, 20%), chills (5%, 19%), abdominal pain (6%, 8%), injection site pain (6%, 8%), infection (4%, 7%), injection site inflammation (2%, 6%), chest pain (2%, 5%), injection site reaction (1%, 3%), toothache

(1%, 3%), depression (14%, 18%), dizziness (12%, 14%), upper respiratory tract infection (12%, 14%), sinusitis (12%, 14%), bronchitis (5%, 8%), nausea (19%, 23%), myalgia (22%, 29%), arthralgia (6%, 9%), urinary tract infection (15%, 17%), urine constituents abnormal (0%, 3%), alopecia (2%, 4%), eye disorder (2%, 4%), injection site ecchymosis (4%, 6%), anemia (1%, 4%), migraine (3%, 5%), vasodilation (0%, 2%). As some of these symptoms may occur following virus infection, it may be difficult to know whether they are due to the administration of IFN  $\beta$ -1a or the patient's underlying condition

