#### **16. Analysis of Final Data**

The initial results of the pilot trial will determine if it should be extended (extension to 100 participants per this protocol) and whether a larger multicenter study will be appropriate. Determining factors will be safety and, if possible with the small sample size, a trend toward efficacy when compared to the standard of care regimen. In addition, the effect of the treatment regimen on viral detection will be examined.

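### The only defined study stopping rule is one on-therapy death individually judged drug-related; no aggregate all-cause mortality review is scheduled between the staggered first ten patients and the end of the pilot

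*Protocol*

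**What the plan says.** Protocol section 8.4 has a line for study stopping rules and gives one entry: "A patient dies during therapy as a result of an SAE assessed as related to the investigational product". Under SAE Reporting in section 8.3, relatedness is judged event by event: "All AEs and SAEs will be evaluated by the investigator or delegate for causal relationship to the investigational product".

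The neighbouring sections describe how hard that judgement may be. Section 8.2 thinks it likely that "this drug will cause certain flu-like symptoms or symptoms compatible with disease progression". Its adverse event list ends with the remark that, for some of the symptoms, "it may be difficult to know whether they are due to the administration of IFN" or to the underlying condition. Section 8.1 states that "special consideration will be placed to determine whether the treatment regimen adversely affects disease progression".

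Aggregate information is planned but is not linked to the stopping rule. Section 8.4 says "Safety monitoring for this interventional study will involve collection of data with direct comparison between IFN" patients and patients not given IFN, without timing or threshold. Section 8.3 requires deaths on therapy or within 30 days of the last dose to be reported, and section 9.3 makes all-cause death a tertiary endpoint.

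Other safeguards exist. For the first ten treated patients, "a staggered administration schedule will be used to minimize the effect of any unforeseen serious adverse events in this patient population" (section 2.3.2). Section 16 provides for "extension to 100 participants per this protocol", to be decided on the initial pilot results with safety a determining factor. Section 12 allows the study to be discontinued on new data or on regulatory advice.

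**The concern.** The protocol puts background fatality at 57-90% (section 1.1). If IFN hastened or added deaths, each such death could look like an ordinary Ebola death, and the harm would show mainly in the death count across patients. The one predefined rule does not use that count. It uses a case-by-case causal judgement of the kind that section 8.2 says may be difficult. The rule can therefore stay silent while mortality rises. It can also stop a harmless drug on one misattributed death.

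**Working it through.** **Nothing to reproduce.** The protocol gives no operating characteristic for its rule, and section 10.1 disclaims a calculated sample size. The figures below illustrate how the rule behaves.

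**Inputs from the protocol**
- Pilot size 30-50 (section 10.1); possible extension to 100 (section 16).
- Background fatality 57-90% (section 1.1).
- Crude deaths over cases in Table 1: Guinea 1214/2047 = 59%, Liberia 2963/7082 = 42%, Sierra Leone 1267/6190 = 20%.

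**Assumed, not in the protocol**
- IFN raises fatality by 20 points.
- Each excess death has probability a of occurring on therapy and being judged drug-related.
- Deaths that would have occurred anyway are never judged related.

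**Step 1: chance that the written rule fires.** P = 1 − (1 − 0.20 × a)^n, with n = 50:
- a = 0: 0%
- a = 0.02: 1 − 0.996^50 = 18%
- a = 0.05: 1 − 0.99^50 = 40%
- a = 0.10: 1 − 0.98^50 = 64%

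With n = 30 the last three become 11%, 26% and 45%. A smaller harm, 59% to 75%, gives for n = 50: 1 − (1 − 0.16 × 0.05)^50 = 33% at a = 0.05, and 1 − (1 − 0.16 × 0.10)^50 = 55% at a = 0.10. At a = 0.50 the same harm is caught in 98% of trials. The result depends almost wholly on a.

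**Step 2: does the rule separate harm from no harm?** Suppose attribution cannot distinguish drug deaths from disease deaths, and 2% of all deaths are called related. For n = 50:
- fatality 59% (harmless drug): 1 − (1 − 0.59 × 0.02)^50 = 45%
- fatality 79% (20 points worse): 1 − (1 − 0.79 × 0.02)^50 = 55%

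Under that assumption the rule hardly discriminates.

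**Step 3: is an aggregate review feasible at this size?** As an illustration only, take looks after 10, 20, 30, 40 and 50 patients. At each look, pause if the death count reaches the smallest number with an upper binomial tail below 0.04 at 59% fatality, which gives 10, 17, 23, 30 and 37 deaths. Exact sequential binomial calculation gives:

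| True fatality on IFN | Pause by 50 patients |
|---|---|
| 59% | 5.6% |
| 70% | 44% |
| 79% | 89% (73% by 30 patients) |
| 80% | 92% |

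At 79% the mean number treated is about 30.

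**Step 4: sensitivity to the reference rate.** The same table shows the weakness of any fixed boundary. If background fatality is really 70% or 80%, both inside the protocol's own range, a harmless drug is paused in 44% or 92% of trials. If background is lower, harm is missed: a rise from 40% to 60% is paused in 7% of trials, and a rise from 45% to 65% in 20%.

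**The case against.** A reader might infer more than the text supports, in three ways.

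- *That drug effects and Ebola cannot be told apart.* Section 8.2 says only that this may be difficult, and says it of some symptoms on an adverse event list, not of deaths. Sections 8.1, 8.2, 8.3 and 12 all rely on attribution being made.
- *That IFN could run to 50 or 100 patients without a pause.* The first ten are started one after another, each once the previous patient has had five doses: nine intervals of about five days, 9 × 5 = 45 days. Same-day starts then require the opinion of the treating physician and the Special Access Program that no unforeseen serious adverse event was seen. Extension to 100 follows a look at the pilot results.
- *That non-fatal or unattributed events lead nowhere.* SAEs go to the coordinator and manufacturer within 24 hours, with provision for ministry reporting within 7 days. Section 12 permits discontinuation on new data from this study.

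These points stand against the stronger readings, but they do not close the gap. The section 2.3.2 gate concerns unforeseen events and decides only whether patients may start on the same day. Deaths from Ebola are foreseen, so an excess of them can pass. Section 16 acts after 30 to 50 patients and states no mortality criterion. Section 12 is discretionary.

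It is also fair that 59% may not suit this trial. It is a crude ratio over confirmed and probable cases, whereas section 5.3 also admits suspect cases, limits age to 18-69 and requires symptom onset under 4 days. Section 15 looks to centres across West Africa. That rules out a fixed numeric boundary taken from this review; it does not remove the need for a scheduled look. A charter or analysis plan may hold more detail, but the protocol writes its stopping rules itself and lists only this one.

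**Conclusion.** The point holds as a should-fix. The only predefined stopping rule rests on individual attribution in a setting where the protocol itself expects overlap between drug effects and disease. No aggregate all-cause mortality review is scheduled from the eleventh patient to the end of the pilot. Excess mortality that is not attributed patient by patient triggers nothing predefined. The size given for this, 18% to 64% of 50-patient trials firing under a 20-point harm, rests on an assumed harm and on assumed attribution of 2-10%; with much higher attribution the rule would work. The 59% boundary shows only that an aggregate review can be informative at this sample size. It is not a recommended level.

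**What to change.** Reconcile section 8.4 with sections 8.1 and 8.2. Keep the existing rule and add a scheduled study-level review, for example after every ten IFN patients and again before the section 16 extension. The review would tabulate all-cause deaths to 30 days after the last dose, and related life-threatening events, beside the untreated comparison that section 8.4 already plans. It needs a pause-for-review criterion whose level and reference rate the sponsor sets. The existing reviewers (sponsor-investigator, treating physicians, Special Access Program) could carry it out.

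State the criterion's operating characteristics for 30 as well as 50 patients, over the 57-90% range and the lower country rates in Table 1.

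The cost is protocol wording, a small recurring tabulation of data already collected, and some chance of an unnecessary pause. That chance is small only if the reference rate is close to the truth, which is why the range must be shown.
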